9.7.5 X-Ray Angiography

Peripheral angiography may be used as an alternative to duplex ultrasound in the assessment of arterial stenosis percentage and location, and may be performed during the visit itself or within 30 days prior. Angiography is an imaging technique to diagnose narrowed or blocked peripheral arteries, the hallmark of PAD. Angiograms may or may not include dye for improving image contrast. Angiograms have been used for decades and are considered the gold standard for evaluating vascular disease. Advanced techniques, such as the computed tomographic angiogram (CTA), and digital subtraction angiography (DSA) have gained popularity in recent years and have shown reliable sensitivity and specificity for differentiating extend of disease [31].

9.8 Intraprocedural Data Collection

Patients enrolled in the study who undergo revascularization surgery to address PAD/CLI will have pertinent data collected immediately before, during, and immediately after the surgical procedure. The schedule of events is summarized in Event Schedule B above (section 9.1). The following steps shall be followed:

- Prior to the start of the procedure, the FlowMet-R probe will be attached to the upper extremity for a 30-second recording. Next, the probe will be moved to the great toe of the limb being treated. If this digit is not usable, another digit may be used.
- Once the probe is placed on the digit, flow will be allowed to equilibrate for 30 seconds before checking signal quality to allow transient changes in perfusion to diminish. Signal quality will be

confirmed by observing the presence of a pulse waveform (if one is expected), or by the stability of the flatline (in the case of complete occlusion). The clinician will also ensure that an appropriate amount of light is detected by the FlowMet-R device. The following light intensity values are acceptable: maximum intensity greater than 30 but less than 255 and average intensity greater than 25 but less than 200. The FlowMet-R device will indicate to the clinician if the intensity is outside of proper bounds by displaying a warning. The clinician should then adjust the probe until the warning disappears. After proper placement and collection of the FlowMet-R and sensor have been confirmed, the physician shall be blinded to all outputs during and after the course of the intervention.

- Movement of FlowMet-R probe should be minimized during the procedure to prevent motion artifact and measurement errors.
- If the FlowMet-R probe is accidentally removed during the procedure or if a data quality warning is displayed by the FlowMet-R software (i.e. too much or too little light is being detected), the probe shall be replaced or reseated on the digit it was originally placed on (if possible). If this is not possible, a different digit may be used and this change shall be noted.
- The digit being measured and patient ID should be entered into the Patient Data section of the FlowMet-R software.
- FlowMet-R data saving shall be initiated prior to state of surgery. Therapies and notable events for each procedure, including timing, shall be recorded.
- The surgical procedure shall take place as per the standard of care.
- At the end of the procedure, FlowMet-R data saving shall be ceased.
- FlowMet-R data, along with angiographic films, and other pertinent information related to the surgical procedure such as patient symptoms and visual assessment shall be uploaded to the registry EDC.

9.9 Deviation Handling

A study deviation is defined as an event within a study that did not occur according to the clinical investigation plan or clinical trial agreement.

Prior approval by Medtronic is expected in situations where the investigator anticipates, contemplates, or makes a conscious decision to deviate. Prior approval is not required when a deviation is necessary to protect the safety, rights or well-being of a subject in an emergency or in unforeseen situations beyond the investigator's control (e.g. subject failure to attend scheduled follow-up visits, inadvertent loss of data due to computer malfunction, inability to perform required procedures due to subject illness). Any deviation from this protocol will be noted and described in the EDC system under the deviations from protocol section.

9.10 Subject Exit, Withdrawal or Discontinuation

The study exit form should be completed at the time a subject is exited from the study. A subject will be considered to have exited from the study for any of the following reasons.

- Subject completes follow-ups required by the investigational plan
- Subject dies

- Subject requests to be withdrawn
- Physician requests that patient be withdrawn to protect the welfare of the patient
- Subject is lost to follow-up

A subject may elect to withdraw from the study at any time. The subject should notify the investigator. The investigator and research staff should encourage all subjects to return for required follow-up visits. Every attempt must be made to ensure all subjects complete the follow-up schedule. For subjects who fail to appear for a scheduled study visit, the site must contact the subject in a timely manner to reschedule the visit and associated required evaluations within the subject's window, if possible.

10. Risks and Benefits

10.1 Potential Risks

The FlowMet-R is FDA cleared and Medtronic (previously LAS) has determined that the FlowMet-R should be classified as a non-significant risk device. There are no incremental risks introduced to the subject as a result of participation in this study.

10.2 Risk Minimization

The potential risks associated with the FlowMet-R have been successfully mitigated. Any potential risks associated with this study are further minimized by selecting qualified investigators and training study personnel on the CIP.

Prior benchtop, animal, and clinical studies have been performed previously.

The FlowMet-R has been validated on the benchtop using an artificial digit coupled with a syringe pump. When the FlowMet-R was used to measure the flow of a blood-simulating fluid through the artificial digit at controlled volumetric flow rates representing the known physiological range, the FlowMet-R output exhibited a linear response with respect to the known volumetric flow rate ($R^2=0.999$).

Additionally, the FlowMet-R has been tested in animal studies on New Zealand white rabbits and Yorkshire pigs. New Zealand white rabbits ($n=5$) undergoing cyanide poisoning and resuscitation have been monitored using the FlowMet-R for the purpose of assessing peripheral blood flow. Yorkshire pigs ($n=3$) undergoing anesthesia have been monitored using the FlowMet-R to assess blood flow within various regions of the pig's core and extremities. In both studies, the FlowMet-R was used to detect increased blood flow during periods of known vasodilation and decreased blood flow during periods of known vasoconstriction and periods of measured decreases in cardiac output.

The FlowMet-R has been used previously as a non-significant risk device to study peripheral blood flow in five IRB-approved studies without adverse events. The first study ($n=37$) was a validation study performed at the University of California, Irvine (UCI IRB HS# 2006-4876). The protocol compared blood flow measurements during before, during, and after brachial artery occlusion using both the FlowMet-R and a laser Doppler system (Perimed Periflux). The study demonstrated a significant correlation between FlowMet-R and the laser Doppler systems (all trials showed $R > 0.7$). A second study ($n=47$) aimed to correlate the FlowMet-R to the degree of wound in healing in patients with chronic wounds. This study was performed as Good Samaritan Hospital, San Jose CA (GSH FWA# 00006889). A third study (ongoing) at UCI (HS#: 2016-3286) is designed to measure blood flow dynamics in patients under anesthesia. A fourth study at the Vascular and Interventional Specialists of Orange County (VISOC)

outpatient clinic in Orange, CA, collected correlative data between FlowMet-R, Rutherford category, ABI, and TBI in 100 patients (WIRB #1177294). A fifth study was conducted at the Cleveland Clinic, with results presented at ACC March 2018. The final two aforementioned studies found that FlowMet-R data could be used to produce a metric which is significantly correlated to TBI and ABI. In totality, these studies suggest that FlowMet-R measurement are correlated to existing standards used to assess vascular functionality and they provide evidence supporting the safety for FlowMet-R. No adverse events have been reported in any study.

10.3 Potential Benefits

There are no anticipated benefits from participation in this study. The information gained from this study could result in improved management and diagnosis of PAD and CLI.

10.4 Risk-Benefit Rationale

The FlowMet-R is FDA cleared and has been classified as a non-significant risk device.

11. Adverse Events and Device Deficiencies

11.1 Adverse Events

Investigators shall submit a report of any device-related or suspected device-related adverse or serious adverse event to the sponsor and IRB as soon as possible, but in no event later than 5 business days after the investigator first learns of the event (§ 812.150(a)(1)). These reports shall be uploaded to the EDC system and will only include adverse events that could reasonably be associated with use of the FlowMet device. All Adverse Events reported to the Sponsor during the study will be reviewed and adequately reported to comply with applicable regulations (ISO 14155):

and vigilance requirements. All adverse events will be classified according, at a minimum, to ISO 14155: . Medtronic will also determine whether a reported Adverse Event is anticipated or unanticipated. Investigators will be asked to classify whether an adverse event is considered serious or non-serious and whether it is considered device related. If an event is determined to be Serious and device related, investigators will be asked to make a determination as to whether or not the study can remain an NSR study. If needed, this determination will be submitted to the IRB. Potential complications are listed in section 6.2. Unexpected complications are also possible, as any electronic device carries some medical risk. Potential complications include slight discomfort due to warming of the interrogated tissue during normal function of the internal components (approximately <1% probability).

Potential complications include slight discomfort due to warming of the interrogated tissue during normal function of the internal components (approximately <1% probability).

12. Statistical Design and Methods

12.1 General Aspects of Analysis

12.1.1 Sample Size

The rate of PAD and CLI within the population seen at a typical vascular clinic is estimated from prior investigation (i.e WIRB #1177294). In this previous study, 100 limbs were assessed using the ABI and graded using the Rutherford classification scheme. PAD (diagnosed via ABI score of <0.9) was present in 63% of limbs. CLI (estimated as having a Rutherford category of ≥ 4) occurred in 15% of limbs. FlowMet-R data was also collected from the above limbs, and the data analysis techniques used in the data analysis section below were applied to build a diagnostic model for PAD and CLI. ROC curves were then generated for the diagnosis of both Claudication and CLI. The resulting area under the curve (AUC) for these ROC curves was 0.67 and 0.80, respectively. However, the Claudicant group AUC had a tighter confidence interval due to larger sample size (84 vs. 22).

Using a conservative estimation that the AUC for distinguishing PAD groups from healthy controls remains within ± 0.05 of the Claudicant group, and ± 0.2 of the CLI group, an estimate for the necessary sampling size can be determined. A standard type I error rate (α) of 0.05 and power of 0.8 is desired, thus the following approximate sample size was calculated for statistically significant results [32, 33]: 160 control limbs and 240 limbs with PAD, of which at least 54 limbs with Claudication and at least 100 limbs with CLI. Limbs with CLI may be included as a subset of limbs with PAD. A minimum of 250 patients (400 limbs) and maximum of 400 patients will be enrolled in the study.

12.1.2 FlowMet-R data analysis and diagnostic model

FlowMet-R data is comprised of continuous blood flow data recorded over 30 seconds. Over this time, a pulsatile blood flow waveform may be present due to the subject's cardiac cycle, provided that digital blood flow is sufficient to generate such a signal. Thus, a combination of the flow amplitude and one or more features of the waveform may be used as inputs to train the predictive model.

The target outcome variable for training the model shall be a continuous metric of PAD severity, analogous to the ABI or TBI. The training will be performed as a regression using iterative algorithms ubiquitous in machine learning.

The predicted outputs from the regression model will be used to generate an ROC curve by classifying a binary diagnostic (i.e. PAD true/false, CLI true/false), or prognostic (i.e. vascular intervention likely within 6 months (true/false)). The classification algorithm which results in the highest diagnostic area under the curve for PAD and CLI shall be chosen to compute final sensitivity and specificity.

A k-fold cross validation scheme will be implemented to gauge model generalization. k-fold cross validation is a statistical sampling method that can be used to train and objectively validate the above

classification algorithms [34]. Using this scheme, only a subset of the total body of collected data is used to train the model, which is then applied to the remaining data withheld from training prospectively. During this validation stage, the performance and generalizability of the model can be assessed. Cross validation allows more objective selection of the optimal algorithm because performance assessment is based upon applying the model to a data set which it is naïve to (i.e. a prospective application of the model).

12.1.3 Analysis of Stenosis

For each artery measured using duplex ultrasound or arterial angiography, the ratio of the PSV distal to the most prominent stenosis to the PCV proximal to the stenosis will be computed (if applicable). The percent stenosis in such arteries will be computed two ways: (1) Percent stenosis = $PSV_{distal}/PSV_{proximal}$, or (2) using the diameter reduction value from Table 3, reprinted from [35].

	Diameter reduction	Waveform	Special broadcasting	PSV distal/PSV proximal
Normal	0	Triphasic	Absent	+++ No change
Mild	1%–19%	Triphasic	Present	<2:1
Moderate	20%–49%	Biphasic	Present	<2:1
Severe	50%–99%	Monophasic	Present	>2:1*

PSV, Peak systolic velocity.

* > 4:1 suggests >75% stenosis, >7:1 suggests > 90% stenosis.

Table 3: Criteria for determining arterial stenosis using peak systolic velocity (PSV) measurements.

Classification of the percent stenosis or presence of greater than 50% stenosis for each limb (used to generate corresponding ROC curve or correlation coefficient) may be determined by either considering a single artery of interest or by considering the artery in each limb with the greatest percent stenosis.

13. Ethics

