9.7.4 Duplex ultrasound

Color duplex ultrasound measurements shall be used to determine stenosis percentage and location, either during the visit itself or within 30 days prior of the patient visit. Duplex shall be acquired from all limbs enrolled in the study with PAD/CLI as defined via the definitions in Section 8.4. If duplex ultrasound is not available, X-ray angiography will be considered a suitable alternative for calculation of stenosis and location. Color duplex ultrasound imaging will be performed in a similar fashion as the study by Lewis, et al. [30]. First, the distal common femoral artery (CFA) will be imaged and the Doppler waveform (DW) assessed visually for any loss of triphasic flow due to significant iliac disease. If the DW shows indications of this, then the iliac arteries will be assessed for the presence of atherosclerotic disease. The scan will continue distally from the CFA assessing the superficial femoral artery (SFA), popliteal, anterior tibial, posterior tibial, and peroneal arteries in the longitudinal plane. The extent and severity of any arterial disease are assessed by measuring the peak systolic velocity (PSV) from the DW just proximal to and distal through the stenosis. For each measured artery, if perceptible stenosis exists, the location of maximum stenosis will be identified and PSV values distal and proximal to the arterial stenosis will be noted on the CRF. The shape of the waveform (i.e. monophasic, biphasic, or triphasic) measured distal to the stenosis shall also be noted. If no stenosis is noted, this will be indicated on the CRF.

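### The protocol does not fix where the numerator of the duplex velocity ratio is sampled, and a truly downstream velocity cannot grade stenosis by Table 3

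*Protocol*

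**What the plan says.** Protocol 9.7.4 (Duplex ultrasound) uses three wordings in successive sentences.

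- Severity is assessed by "measuring the peak systolic velocity (PSV) from the DW just proximal to and distal through the stenosis".
- For each artery with visible stenosis, "PSV values distal and proximal to the arterial stenosis will be noted on the CRF".
- The waveform shape "measured distal to the stenosis shall also be noted".

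Protocol 12.1.3 (Analysis of Stenosis) then says that "the ratio of the PSV distal to the most prominent stenosis to the PCV proximal to the stenosis will be computed". PCV is presumably a slip for PSV. Percent stenosis is to be obtained in two ways: (1) by setting it equal to the distal/proximal PSV ratio, or (2) by "using the diameter reduction value from Table 3". The table's ratio column is also labelled distal over proximal. It gives no change for a normal artery, <2:1 for the mild and moderate bands (up to 49%) and >2:1 for the severe band (50%–99%). Its footnote adds "> 4:1 suggests >75% stenosis, >7:1 suggests > 90% stenosis".

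The result feeds two secondary endpoints in Protocol 4.1.2.1: the ROC curve for stenosis above 50%, and the correlation with greatest percent stenosis. SAP 7.10.2 refers to both but gives no derivation of stenosis. SAP 7.3 pools all centres.

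**The concern.** Velocity rises where the lumen is narrow and falls again where the vessel regains its calibre. A ratio that climbs with severity therefore needs a numerator taken in, or right at, the narrowing. The recording instruction and the formula instead name a velocity distal to the stenosis. The next sentence of 9.7.4 uses the same phrase for the waveform, where it naturally means downstream. A site could reasonably enter a downstream value, while another site, relying on the earlier description of sampling through the stenosis, enters the in-stenosis peak.

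At stake is the reference label for the stenosis analyses. If the label does not follow severity, or follows it at some sites only, the stenosis AUC and correlation are distorted for reasons unrelated to the device.

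**Working it through.** **Plan's own figures.** The Table 3 cut-offs (2:1, 4:1, 7:1) are reprinted from a cited source and the protocol gives no formula for them, so they cannot be reproduced from the documents. The check concerns direction: which numerator can move with severity at all.

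**Assumption (not in the documents).** Flow continuity, meaning that velocity times lumen area is constant. Let s be the fractional stenosis, q the share of proximal flow still in the vessel downstream, and r the downstream/proximal lumen diameter.

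- In-stenosis/proximal ratio: 1/(1−s)² if s is diameter reduction, 1/(1−s) if s is area reduction.
- Fully downstream/proximal ratio: q/r². It does not contain s.

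| s | In-stenosis, s as diameter | In-stenosis, s as area | Downstream, q = 1, r = 1 |
|---|---|---|---|
| 20% | 1.56 | 1.25 | 1.0 |
| 50% | 4.0 | 2.0 | 1.0 |
| 75% | 16 | 4.0 | 1.0 |
| 90% | 100 | 10 | 1.0 |

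Both in-stenosis forms rise with s. The area form meets the 2:1 and 4:1 cuts at 50% and 75%, but gives 10 rather than 7 at 90%. The diameter form, which is the table's stated scale, exceeds all three cuts.

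**Range for the downstream ratio.** Assume q from 0.5 to 1 and r from 0.75 to 1.1.

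- Lowest: 0.5/1.1² = 0.41.
- Highest: 1/0.75² = 1.78.
- With q = 1, reaching 2:1 requires r = 1/√2 = 0.707, a downstream lumen about 29% narrower than the proximal one.

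**What each method does with a downstream value.**

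- Method (2), ratio column: 0.41 to 1.78 is below 2:1 at every severity, so a 50%–99% stenosis falls outside the severe band.
- Method (1): a ratio of 1.0 reads as 100% stenosis, and any ratio above 0.5 reads as more than 50%. Within the assumed range, the ratio is 0.5 or less only when about half the flow is lost and the downstream calibre is about equal to or wider than the proximal one. Nearly every artery is called significant.

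The two methods err in opposite directions. Method (1) also conflicts with Table 3 when the numerator is in-stenosis: the table's 2:1 cut becomes 200%.

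**Illustration of AUC loss.** Assume 160 truly stenosed limbs, N true negatives, a true AUC of 0.80, and k stenosed limbs labelled negative independently of the device value. Then m = k/(k+N) and AUC = 0.5m + 0.80(1−m).

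| k | N = 80 (imaged limbs only) | N = 240 (adding the 160 control limbs) |
|---|---|---|
| 32 (20%) | m = 0.286, AUC 0.714 | m = 0.118, AUC 0.765 |
| 80 (50%) | m = 0.500, AUC 0.650 | m = 0.250, AUC 0.725 |

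None of the inputs 160, 80, 0.80, 20% or 50% comes from the documents for this endpoint.

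**The case against.** The strongest reply is that the plan, read as a whole, already means the in-stenosis peak. Protocol 9.7.4 describes sampling through the stenosis and has the operator find its point of maximum. Table 3 gives the distal/proximal label to a ratio that rises with severity, so distal may simply be this protocol's name for the raised velocity. A sample just beyond the narrowing could also still be elevated. This stands as far as it goes: the text is ambiguous, not uniformly downstream. It does not remove the problem, because the recording instruction and the formula both drop the word through and neither names an in-stenosis value.

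A reader might infer that severe stenoses will all be labelled negative. The documents do not support that. The direction holds only for the ratio column of method (2); method (1) pushes the same artery to positive. A monophasic waveform could also place it in the severe row, and no rule says which column governs.

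It is also fair to object that simple continuity on diameter does not reproduce Table 3's cut-offs. Under it, a ratio of 2 corresponds to a 29% reduction, and a 75% reduction gives 16. The model therefore supports the direction of the argument, not its calibration. The CRF itself is not among the documents either, so the field's actual label is unknown.

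**Conclusion.** The concern holds as an unresolved inconsistency with a real consequence. The protocol's wordings do not agree on the numerator, and a fully downstream velocity cannot track the severity that Table 3 grades. On that reading the two permitted methods give nearly opposite labels, and differences between sites would be absorbed by pooling. The conclusion rests on flow continuity; the value of about 1 also needs similar calibre and preserved flow, and 0.41 to 1.78 is the range when these are relaxed as shown.

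The reach is limited. Only limbs graded by duplex are touched, since angiography may be used instead and yields no PSV. Only the secondary stenosis ROC and correlation depend on the label, and SAP 7.2 presents results descriptively. The primary AUC and the sample size are unaffected. A reader might take 0.65 to 0.77 as the expected stenosis AUC; those figures only illustrate how mislabelling would act and should not be cited as a predicted loss. The matter should be corrected because it is cheap to do so and the secondary stenosis results cannot be interpreted without it.

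**What to change.** - Check the label of Table 3's ratio column against the source from which it is reprinted.
- Then use one definition in Protocol 9.7.4, the CRF field, Protocol 12.1.3 and the SAP: highest PSV within the stenosis divided by PSV just proximal to it. Correct PCV to PSV.
- State in the SAP that the >50% label uses this ratio with Table 3, so that method (1) no longer offers a conflicting answer.
- For limbs already recorded, take the in-stenosis PSV from the duplex report where it is available. Where only a downstream PSV exists, set the ratio-based label to missing, not to below 50%.

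The cost is wording in two protocol sections, a CRF label and a short SAP passage, plus some checking of records. Prospectively no extra scan should be needed, because 9.7.4 already describes sampling through the stenosis. The documents do not say whether stored reports hold the in-stenosis value, so a few limbs may lose their ratio-based label.

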7.10.2 Secondary Objectives

The secondary endpoints will be analyzed as follows:

1. The capability of the acceleration time from the FlowMet-R device to predict a vascular intervention or amputation will occur within three and six months following initial visit will be determined using the AUC from an ROC curve where the endpoint is vascular intervention or amputation within 7 months, which is the end of the 6 month follow-up window. The 95% CI of the AUC will be derived using the method described in DeLong, et al (1998) [15].
2. The capability of the acceleration time from the FlowMet-R device to predict a $\geq 50\%$ stenosis determined using the AUC from an ROC curve where the endpoint is vascular intervention or amputation within 7 months, which is the end of the 6 month follow-up window. The 95% CI of the AUC will be derived using the method described in DeLong, et al (1998) [15].
3. The correlations between the acceleration time from the FlowMet-R device and peripheral artery stenosis, changes in ABI, and changes in TBI will be computed using Pearson correlations. The changes for ABI and TBI will be as follows: 0 to 3 months, 0 to 6 months, and 3 to 6 months.
4. The correlation between the acceleration time from the FlowMet-R device and changes in Rutherford Classification will be computed using the Spearman correlation. The changes for Rutherford Classification will be as follows: 0 to 3 months, 0 to 6 months, and 3 to 6 months.

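### Method 1 for percent stenosis in protocol 12.1.3 is a velocity ratio that contradicts the table beneath it, and neither document fixes the stenosis variable for the secondary ROC and correlation

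*Protocol*

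**What the plan says.** Protocol 12.1.3 opens with one rule for both imaging methods: "For each artery measured using duplex ultrasound or arterial angiography, the ratio of the PSV distal to the most prominent stenosis" to the velocity proximal to it is to be computed, where applicable. It continues: "The percent stenosis in such arteries will be computed two ways". Method 1 sets percent stenosis equal to distal PSV divided by proximal PSV. Method 2 takes the diameter reduction from the table in that section, captioned "Criteria for determining arterial stenosis using peak systolic velocity (PSV) measurements". (The protocol uses the number Table 3 twice. The visit-window table in 9.3 is not meant here.)

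That table gives:
- normal: 0 diameter reduction, triphasic waveform, no change in velocity
- mild: 1–19%, triphasic, ratio below 2:1
- moderate: 20–49%, biphasic, ratio below 2:1
- severe: 50–99%, monophasic, ratio above 2:1, with the footnote "> 4:1 suggests >75% stenosis, >7:1 suggests > 90% stenosis"

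The result is used directly. "Classification of the percent stenosis or presence of greater than 50% stenosis for each limb" supplies the ROC curve or the correlation coefficient, and may be based on a single artery of interest or on the worst artery in the limb.

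Protocol 9.7.5 adds that "Peripheral angiography may be used as an alternative to duplex ultrasound in the assessment of arterial stenosis percentage and location". SAP 7.10.2 item 3 says that correlations of acceleration time with "peripheral artery stenosis, changes in ABI, and changes in TBI will be computed using Pearson correlations". The secondary endpoint in section 4.1.2.1 of both documents sets the threshold at more than 50%, whereas SAP 7.10.2 item 2 uses 50% or more.

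**The concern.** A ratio of two velocities is not a percentage of narrowing, and the table in the same section shows how far apart the two are. If an analyst follows method 1 literally, the 50% threshold no longer marks significant stenosis, and the secondary ROC curve answers a different question from the one posed.

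The choice of method is also left open. Two methods, two imaging techniques and two ways of picking the artery are allowed, and no rule assigns them to the ROC or to the correlation. The analyst would have to choose after seeing data. At stake are two secondary results: discrimination of significant stenosis, and correlation with the greatest percent stenosis.

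**Working it through.** **Inputs.** The method 1 formula, the table and its footnote are all in protocol 12.1.3. The threshold is more than 50% (section 4.1.2.1 of both documents). What is recorded at duplex comes from protocol 9.7.4.

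**Step 1: the plan's own mapping.** The table and footnote put no change at 0%, the 2:1 boundary at 50%, the 4:1 boundary at 75% and the 7:1 boundary at 90%.

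**Step 2: method 1 at the same points.** Percent stenosis = distal PSV / proximal PSV, written as a percentage (×100) or left as a raw number.

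| Ratio | Table | Method 1 ×100 | Over 50%? | Method 1 raw | Over 50? |
|---|---|---|---|---|---|
| 1 (no change) | 0% | 100% | yes | 1 | no |
| 2 | 50% | 200% | yes | 2 | no |
| 4 | 75% | 400% | yes | 4 | no |
| 7 | 90% | 700% | yes | 7 | no |

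Method 1 reproduces none of the four points. On either reading the answer to the 50% question is the same in every row.

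**Step 3: could another formula have been meant?**
- Inverse ratio, 100/ratio: 100, 50, 25, 14.3%. This falls as disease worsens.
- 1 − 1/ratio: 0, 50, 75, 85.7%. This matches the first three points, but gives 85.7% at 7:1, where the footnote implies 90%. It is not stated in either document.

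Neither rescues the text as written.

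**Step 4: what method 1 would do to the ROC.** Protocol 9.7.4 has PSV values noted only where stenosis is perceptible; otherwise its absence is marked on the CRF. Read as a percentage, method 1 therefore puts mild, moderate and severe arteries with a ratio of about 1 or more together as positive, against arteries with no stenosis noted. The curve would describe any perceptible stenosis. Read as a raw number, no tabulated duplex ratio is positive at all.

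**Step 5: which variable enters the analyses.**
- 12.1.3 offers both methods for the same arteries and assigns neither to an analysis.
- PSV is described in 9.7.4 as read from the Doppler waveform. Nothing in the documents has angiography yielding a PSV, so method 1 is unavailable for limbs with angiography only.
- Method 2 yields bands such as 50–99%, not the continuous value that a Pearson correlation assumes.
- SAP 7.7 and 7.8 define ABI, TBI and acceleration time. No SAP section defines stenosis.
- SAP 7.1.3 uses one full analysis set for all analyses and does not separate imaging methods.
- SAP 7.10.2 item 2 introduces prediction of stenosis, but then names vascular intervention or amputation within 7 months as the ROC endpoint.

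**The case against.** Four counter-arguments deserve weight.

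- **The plan already contains a workable rule.** Method 2 places severe stenosis at a ratio above 2:1 and can be read from duplex findings. The ROC fails only if method 1 is used. This is true, but method 1 is listed first and nothing tells the analyst to avoid it.
- **Negatives still exist under method 1.** A reader might infer that every artery would exceed 50%, leaving the ROC without a negative group. The documents do not support that. Arteries without perceptible stenosis need not receive a ratio, and healthy-cohort limbs with normal ABI and TBI are assumed free of significant stenosis (protocol section 5, SAP section 5). The defect is narrower: grades of stenosis cannot be separated.
- **Pooling is not stated.** A reader might infer that duplex limbs get the ratio, angiography limbs the diameter reduction, and that both then enter one Pearson correlation. The text makes no such split. Both methods are offered for the same arteries, and computing in two ways can equally mean two separate analyses. What stands is that mixing is not excluded.
- **The stakes are limited.** These are secondary endpoints, and SAP 7.2 says that the objectives are not hypothesis-driven and will be presented descriptively. The SAP does not repeat method 1. That limits the consequence but leaves the stenosis variable undefined.

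**Conclusion.** Method 1 is wrong as written. It contradicts the table in its own section at all four reference points: 100%, 200%, 400% and 700% against 0%, 50%, 75% and 90%. With it, the 50% cut cannot distinguish mild or moderate from severe stenosis. This is arithmetic on the plan's own figures and needs no assumption beyond reading no change as a ratio of about 1.

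The second part is a gap in specification. The documents do not fix which method, or which artery for the ROC, enters the analyses, and method 2 does not supply a continuous value for the Pearson correlation. Combining incompatible scales is a risk left open, not a stated plan. Its effect on the correlation cannot be sized from the documents, which give neither the share of limbs with angiography nor the distribution of ratios.

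The point concerns the secondary stenosis ROC and stenosis correlation only. The primary AUC analysis and the sample size are unaffected.

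**What to change.** 1. Delete method 1 from protocol 12.1.3.
2. Classify every artery on one ordered, non-overlapping scale built from the table there: no stenosis; 1–19%; 20–49%; 50–75% (ratio above 2:1 up to 4:1); above 75% up to 90% (above 4:1 up to 7:1); above 90% (above 7:1).
3. For duplex, use PSV ratio and waveform together, because mild and moderate share the ratio below 2:1 and only the waveform separates them. State what happens when ratio and waveform disagree. For angiography, bin the diameter reduction into the same classes. Take a CRF entry of no stenosis as the lowest class.
4. State where exactly 2:1, exactly 50%, values between the printed bands and total occlusion belong. The table leaves 2:1 unassigned and stops at 99%.
5. Define significant stenosis by the table's severe band, and use one threshold in both documents in place of more than 50% in section 4.1.2.1 and 50% or more in SAP 7.10.2 item 2.
6. Use the worst artery per limb throughout, and Spearman instead of Pearson correlation for stenosis.
7. Put this definition in SAP 7.10.2, and correct item 2 so that the ROC endpoint is stenosis rather than intervention or amputation within 7 months.

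The cost is protocol and SAP wording. No new data are needed: protocol 9.7.4 already has PSV, waveform and absence of stenosis recorded, and 9.7 and 9.7.5 already allow a stenosis percentage from angiography. The price is a coarser, ordinal measure of stenosis.
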